5.3.1 Demographics, Other Baseline Characteristics and Medication

Summary statistics will be provided by treatment arm and overall (if applicable) for baseline characteristics and demographic variables; summaries will be provided on the mITT population. Prior and concomitant medications will be reported for the Safety population.

5.3.1.1 Demographic Characteristics

Descriptive statistics by treatment arm and overall (if applicable) will be performed for the demographic characteristics and disease history. Listings will also be presented for the demographic characteristics and disease history, respectively.

5.3.1.2 Fibroscan

A Fibroscan will be conducted at screening/re-screening visit if it was not performed within the prior 12 months of the corresponding visit. The Fibroscan is not required if no fibrosis was seen on liver biopsy within 2 years prior to screening/re-screening visit.

Result of Fibroscan (reported in kPa) will be summarized by treatment arm and overall. Summaries will be performed for all patients together regardless of the time that the Fibroscan was conducted (either within the prior 12 months of screening/re-screening or at the moment of screening/re-screening).

Number of patients with a liver biopsy performed within 2 years prior to screening will be summarized.

For re-screened patients, only information in the re-screening visit will be analyzed.

All data collected related to Fibroscan will be listed.

5.3.1.3 Hepatitis B Genotyping

HBV genotyping will be performed at screening/re-screening if it has not been documented in the prior medical record. HBV Genotype testing by means of PCR will be summarized by treatment arm and overall.

For re-screened patients, only information in the re-screening visit will be analyzed If the value in the re-screening visit is not valid (ie: "CANCELLED", "Not Detected", "Unknown") but the screening measurement has a valid result, this will be the one used in the summaries.

All data collected related to HBV genotyping will be listed.

5.3.1.4 HCV, HDV and HIV tests

The results of following tests will be summarized by treatment arm and overall:

- Human Immunodeficiency Virus-I antibodies (HIV-I);
- Human Immunodeficiency Virus-II antibodies (HIV-II);
- Hepatitis C virus antibodies (HCV);
- Hepatitis Delta virus antibodies (HDV)

For re-screened patients, only information in the re-screening visit will be analyzed.

All data collected related to HCV, HDV and HIV tests will be listed.

5.3.1.5 Medical History

Medical history abnormalities will be coded to Medical Dictionary for Regulatory Activities (MedDRA) terms. The version used will be specified in the data display footnote. Conditions will be summarized by System Organ Class (SOC) and Preferred Term (PT) by treatment arm and overall. Listings will also be presented.

5.3.1.6 Physical Examination

Results of the complete physical examination assessment performed at Screening will be summarized by system class and by treatment arm and overall:

- Normal
- Abnormal Not Clinically Significant
- Abnormal Clinically Significant

For re-screened patients, only information in the re-screening visit will be analyzed.

The result of the baseline physical exam and the significant findings will be presented by listing.

5.3.1.7 Electrocardiogram (ECG)

Summaries of evaluation (normal; abnormal not clinically significant; abnormal clinically significant) will be provided by treatment arm and overall. Only available data will be used, and missing data at baseline will not be imputed.

For re-screened patients, only information in the re-screening visit will be analyzed.

All ECG results will be listed on a by-patient basis.

5.3.1.8 Vital Signs and Height, weight and BMI

Height, weight and Body Mass Index (BMI) as well as the vital signs at baseline will be described by treatment arm and overall. The variables to be included are:

- Blood Pressure:
 - Systolic (SBP)
 - o Diastolic (DBP)
- Pulse rate
- Body temperature
- Respiration rate

Summary statistics (including number, mean, SD, median, Q1, Q3, minimum, and maximum) for height, weight, BMI and all vital signs at baseline will be calculated by treatment arm and overall (if appropriate). Only available data will be used, and missing data at baseline will not be imputed.

For re-screened patients, only information in the re-screening visit will be analyzed.

Height, weight, BMI and all vital signs measurements will be listed.

5.3.1.9 Laboratory values at baseline

Laboratory assessments at baseline include hematology, serum chemistry and urinalysis.

The summary statistics (including number, mean, SD, median, Q1, Q3, minimum, and maximum) of all quantitative laboratory variables at baseline will be calculated by treatment arm and overall (if appropriate). Only available data will be used, and missing data at baseline will not be imputed. Data will be listed by patient.

For re-screened patients, only information in the re-screening visit will be analyzed.

5.3.1.10 Prior and Concomitant Medications

Prior medications are those that the patient used prior to the date of first dose of study drug. Concomitant medications (including immunosuppressive medications, vaccines, and new HBV treatments) are defined as medications that continued or started on or after the date of first dose of study drug, recorded through Day 169. If start date is after Day 169, they will not be considered in the summaries of concomitant medications. Only immunosuppressive medications, vaccines, and new HBV treatments or medications associated with MAEs, NCIs, SAEs, hepatitis flares, or hepatic injury will be recorded beyond this point. Prior and concomitant medications will be summarized by treatment arm according to the World Health Organization Drug Dictionary (WHO-DD), using the version in effect at the time of database lock (September 2021 or subsequent) and considering the first digit of the Anatomical Therapeutic Chemical

22-Apr-2024

(ATC) classification system and the first 3 digits of the ATC classification system (therapeutic category). Patients will be counted once in each ATC category (anatomical or therapeutic).

Prior and concomitant medications will be summarized separately. Medications recorded after Day 169 will also be summarized separately as Post-Treatment medications.

Listings will also be presented.

5.3.1.11 Other Baseline Variables

Serum pregnancy test, Urine drug and alcohol screen and Eligibility criteria will be listed.

5.3.2 Efficacy Analyses

Analyses of efficacy endpoints will be performed in the mITT population. In addition, sensitivity analyses will be performed in the PP population and will be considered supportive.

All parameters involved in any of the primary, secondary, or exploratory efficacy endpoints will be summarized according to their nature by treatment arm and overall. The original value for these parameters will be listed.

5.3.2.1 Primary endpoint

The primary endpoint will be considered as described in section 4.2.1.

Patients who discontinue early or have missing HBsAg values on Day 169 but who achieve virologic response or serologic clearance of HBsAg on the last available assessment prior to Day 169 will be treated as responders for the primary endpoint; otherwise, patients with early discontinuation or missing HBsAg values on Day 169 will be treated as non-responders.

The proportion of patients achieving virologic response (defined as a 1.0-log reduction in HBsAg or serologic clearance of HBsAg) on Day 169 will be estimated as follows:

(Number of patients having achieved virologic response or serologic clearance of HBsAg to Day 169) / (Number of patients in the corresponding treatment (or overall)) x 100%

This proportion will be compared between treatment groups using Chi-Square Test or Fisher's Exact Test at a 0.05% two-sided level of significance. Fisher's Exact Test will be used if the expected values of at least the 80% of the cells in the contingency table created for estimating proportions are lower than 5.

This proportion will be analyzed using logistic regression models with treatment arm and baseline qHBsAg level as covariate. The analysis of maximum likelihood and odds ratio estimates for patients predicting a 'Yes' in achieving virologic response will be shown.

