10.4. Statistical Methods

10.4.1. Primary Efficacy Endpoint

For the primary analysis, proportions of patients with virologic response, defined as a 1.0-log reduction in HBsAg or serologic clearance of HBsAg, will be compared between HepTcell and placebo groups using Fisher's Exact Test at a 0.05% two-sided level of significance.

Patients who discontinue prematurely or have missing data will be considered nonresponders for that endpoint. Linear and logistic regression will be employed to examine the effects of baseline factors, such as qHBsAg level, HBV DNA levels, and hepatitis B genotype on response.

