10.4.2. Secondary and Exploratory Efficacy Endpoints

The same approach as used for the primary efficacy endpoint will be applied for secondary and exploratory endpoints that are categorical in nature.

Changes from baseline in PBMC ELISpot, HBsAg, HBcrAg, pg-RNA, and quantitative HBV DNA will be analyzed using a mixed model for repeated measures (MMRM). The model will include the fixed effects of treatment, stratification factor, week, and treatment-by-visit interaction as well as the continuous, covariate of baseline level. The model will employ an unstructured within patient covariance matrix and a restricted maximum likelihood (ReML) estimation method.

Relationships between hepatitis flares and HBsAg loss and/or decline will be evaluated logistic and linear regression.

A Kaplan-Meier model will be developed to compare changes between treatment groups in HBsAg clearance and a 1-log reduction in HBsAg over time.

No multiplicity adjustments will be made for secondary or exploratory endpoints.

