10.6. Statistical Analysis Plan

A formal statistical analysis plan (SAP) will be developed and finalized prior to the database lock and unblinding of treatment assignment. This plan will confirm the analysis sets used in the analysis, outline all data handling conventions, and specify all statistical methods to be used for all safety and efficacy analyses. The SAP will be formalized and signed-off on prior to the locking of the database and unblinding of the treatment codes. The SAP will supersede the protocol with respect to analyses specified, although the primary analysis will remain the same. It is anticipated that analyses other than those specified in the protocol may be pre-specified in the SAP.

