2. INTRODUCTION

An interim analysis was conducted at Week 24 that demonstrated that the primary and secondary endpoints of the study were not met. HepTcell was well-tolerated, with no significant safety events.

Per protocol Section 7.2, the Sponsor is terminating the study for lack of efficacy. The IND and respective CTAs will be inactivated, and the investigational product will not undergo further clinical testing. As there were no ongoing MAEs, NCIs or IMCs at the time of termination, safety follow-up will end as of this date. Any accrued efficacy or safety information prior to study termination will be provided in tables and listings only up through the date of study termination.

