5.3 Summary of Statistical Methods

This study is designed as a phase 2 study, exploratory in nature, to evaluate the response to HepTcell in treatment-naïve patients with inactive CHB. Comparisons will be performed between HepTcell and Placebo at a two-sided type I error rate of 0.05 which will not be adjusted for multiple testing.

The study will be considered to have achieved proof-of-concept when the 2-sided p-value is <0.05. Accordingly, the primary and key secondary efficacy endpoints will present 2-sided 95% Confidence Intervals (95%Cls) when applicable.

Unless otherwise specified, efficacy analyses will be performed using the mITT population, where patients will be in the treatment arm to which they received. As described in more detail elsewhere, patients will be analysed according to the treatment of the most treatment received. Moreover, supportive efficacy analyses will be performed in the PP population. Safety related analyses will use the safety population, where patients will be analyzed according to the treatment that they receive.

All applicable baseline data will be summarized by treatment arm (HepTcell, placebo), unless specified otherwise. Safety and efficacy data will also be summarized by treatment arm and additionally by time-point of assessment and/or follow-up, when appropriate.

Continuous variables will be summarized using the number of observations (n), mean (95%CI, if appropriate), standard deviation (SD), Standard error (SE, if appropriate), median, first quartile (Q1), third quartile (Q3), minimum, and maximum along with the total number of patients contributing values.

Descriptive statistics for categorical/qualitative data will include frequency counts and percentages. The denominator for all percentages will be the total number of patients in the treatment arm and dose number (if applicable) within the population of interest, unless stated otherwise in the table footnote.

Change from baseline is calculated only for patients with non-missing values for both the baseline and the time-point of interest and will be missing otherwise.

Statistical comparisons will be performed between HepTcell and placebo at a 5% confidence level.

All relevant patient data will be included in listings. All patients entered into the database will be included in patient data listings. The listings will be generally sorted by treatment arm and then Patient ID, unless specified otherwise.

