5.3.17 Changes to Protocol-planned Analyses

According to the protocol, ECG parameters will be summarized by treatment group and protocol specified collection time point and a summary of change from baseline at each protocol specified time point by treatment group will also be presented. However, ECG parameters have not been collected and they are not available for analyses.

22-Apr-2024

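### The SAP's rule for choosing the primary test can never select Fisher's exact test at about 80 patients, so chi-square replaces the protocol's fixed test without being listed as a change

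*SAP*

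**What the plan says.** Protocol 10.4.1 (and the synopsis) names one test with no selection rule: the responder proportions "will be compared between HepTcell and placebo groups using Fisher's Exact Test". Protocol 10.4.2 extends it: "The same approach as used for the primary efficacy endpoint will be applied for secondary and exploratory endpoints that are categorical in nature". Protocol 10.6 limits what the SAP may alter: "The SAP will supersede the protocol with respect to analyses specified, although the primary analysis will remain the same".

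SAP 5.3.2.1 makes the primary comparison by chi-square or Fisher, and uses Fisher only if "the expected values of at least the 80% of the cells in the contingency table created for estimating proportions are lower than 5". SAP 5.3.2.2.1 (HBsAg clearance) and 5.3.2.2.2 (HBV DNA clearance) repeat the rule. SAP 5.3 ties the trial's conclusion to the result: "The study will be considered to have achieved proof-of-concept when the 2-sided p-value is <0.05".

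SAP 5.3.17, the section for departures from the protocol, covers ECG parameters only: "However, ECG parameters have not been collected and they are not available for analyses". The SAP version history does not mention the primary test either.

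**The concern.** The selection rule looks like a safeguard for sparse data: a reader would expect Fisher's test to apply when responders are few. It cannot, because its condition is out of reach at this sample size. The protocol's unconditional exact test has in effect become an unconditional chi-square test, although the protocol says the primary analysis will stay as it is, and the SAP does not list the change.

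The p-value from this test decides proof-of-concept. With few responders expected on placebo, chi-square and Fisher can fall on opposite sides of 0.05, so the choice of test can decide the conclusion.

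**Working it through.** **Inputs.** About 80 patients, 1:1, 40 per arm; 3% placebo and 25% HepTcell response; two-sided 0.05; approximately 80% power (Protocol 5.1, 6.2 and 10.2; SAP 5.1). Two assumptions are mine: uncorrected Pearson chi-square, since the SAP does not say whether a continuity correction applies, and a set of arm splits around 40/40, since the final analysis numbers are not given.

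**1. The plan's power figure.** Enumerating all 41 x 41 outcomes at 40 per arm gives 78.0% power for Fisher, in line with approximately 80%. Uncorrected chi-square gives 88.5%, and continuity-corrected chi-square 74.7%. The pooled normal approximation gives 82.2%, so the stated figure does not by itself show which test was assumed.

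**2. Can the rule select Fisher?** Eighty percent of 4 cells is 3.2. Three of four is 75%, so all four expected counts must be below 5. The four counts sum to N, so N must be below 20. More precisely, each arm's two counts sum to the arm size, so both arms must be below 10, and the largest possible total is 9 + 9 = 18.

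At 40 per arm, each arm's two expected counts sum to 40, so at most one per arm can be below 5. That is at most two cells (50%), whatever the data. Enumeration at 40/40, 41/39, 42/38, 39/41, 38/42 and 38/38 confirms a maximum of two. At the planned rates the expected counts per arm are 40 x 0.14 = 5.6 and 40 x 0.86 = 34.4.

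**3. One table by hand.** Four responders v none at 40/40:

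- Chi-square = 80 x (4 x 40 - 0 x 36)² / (40 x 40 x 4 x 76) = 2,048,000 / 486,400 = 4.21, p = 0.040.
- Fisher = 2 x C(40,4)/C(80,4) = 2 x 91,390 / 1,581,580 = 0.116.

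Five v none gives 0.021 and 0.055. Six v none gives Fisher p = 2 x 3,838,380 / 300,500,200 = 0.026. With no placebo responders, success therefore needs 4 HepTcell responders under chi-square and 6 under Fisher. Other tables that split the tests include 7 v 1 (0.025 and 0.057) and 10 v 3 (0.034 and 0.066).

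**4. Across splits, at 25% v 3%.**

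| HepTcell/placebo | Responders needed v 0 placebo: chi-square, Fisher | Power: chi-square, Fisher | Chi-square significant only |
|---|---|---|---|
| 40/40 | 4, 6 | 88.5%, 78.0% | 10.4% |
| 38/38 | 4, 6 | 86.8%, 74.6% | 12.2% |
| 41/39 | 4, 6 | 85.6%, 80.5% | 5.1% |
| 42/38 | 5, 6 | 86.0%, 79.9% | 6.2% |
| 39/41 | 4, 5 | 88.1%, 84.2% | 4.0% |
| 38/42 | 4, 4 | 86.8%, 84.9% | 1.9% |

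No table in any split is significant by Fisher but not by uncorrected chi-square. The number significant by chi-square only is 72 at 40/40, 68 at 38/38 and 42 at each of the other four splits.

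**5. Type I error.** The maximum over common response rates is 5.7-5.9% for chi-square and 3.0-4.4% for Fisher across the splits. At 40/40 chi-square peaks at 5.9% for a common rate near 9% (Fisher's maximum is 3.3%). At the planned 3% placebo rate the figures are 1.9% and 0.07%.

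**6. If a continuity correction applies.** No table is then significant by chi-square where Fisher is not. The reverse occurs: 8 tables at 40/40 and 36 at 41/39 are significant by Fisher only.

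**7. If the rule was inverted by mistake.** The usual convention uses Fisher when more than 20% of cells have expected counts below 5. At 40/40 that version has 82.2% power, so it disagrees with Fisher in 82.2 - 78.0 = 4.2% of trials at 25% v 3% (1.2% at 41/39). It would still not be the protocol's fixed test.

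**The case against.** The strongest reply is that the consequence is small. The SAP's introduction reports that "An interim analysis was conducted at Week 24 that demonstrated that the primary and secondary endpoints of the study were not met", and no table is significant by Fisher without also being significant by uncorrected chi-square, so that result cannot be overturned. This stands for the uncorrected test. It does not cover a continuity-corrected one, under which a Fisher-significant table could be missed, and the SAP does not say which was used.

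Chi-square is also not a poor test here. At a common rate of 3% its size is 1.9% while Fisher's is 0.07%, and at 5% they are 4.3% and 0.4%. The 5.9% peak needs a common rate about three times the assumed placebo rate. This stands too: the main fault is non-conformity with the protocol, not an invalid test.

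Protocol 10.6 protects only the primary analysis, so the SAP was entitled to change the test for the two clearance endpoints. That is right. For those endpoints the defects are a rule that cannot operate and no entry in 5.3.17 for the departure from 10.4.2.

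Finally, chi-square is named openly in SAP 5.3.2.1, and the rule may be a slip for the usual convention. But naming it there does not list it as a departure, a programmer must follow the text as written, and the convention would also conflict with the protocol.

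**Conclusion.** The point holds. That the rule cannot select Fisher is arithmetic and needs no assumption beyond an analysis set of at least 20 patients. The conflict with Protocol 10.4.1 and 10.6, and the missing entry in SAP 5.3.17, can be read directly from the documents.

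The size depends on the arm split and on chi-square being uncorrected. Disagreement at the planned rates runs from 1.9% to 12.2% of trials, always towards success. The number of responders needed against none on placebo is the same or up to two lower. Even at 38/42, where that number is equal, 42 other tables still split the tests. Type I error exceeds 5% by less than one percentage point.

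This should be fixed because it concerns the primary analysis and the correction is cheap. It gives no reason to doubt the reported negative result if uncorrected chi-square was used.

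**What to change.** In SAP 5.3.2.1, 5.3.2.2.1 and 5.3.2.2.2, delete the chi-square option and the 80% rule, and state that the proportions are compared between treatment groups by Fisher's exact test at a two-sided 0.05 level. This also removes the printed 0.05%, which conflicts with SAP 5.3 and the sample size section. The same misprint in Protocol 10.4.1 ("compared between HepTcell and placebo groups using Fisher's Exact Test at a 0.05% two-sided level of significance") and its synopsis should be noted as an error for 0.05.

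Report Fisher p-values in final Tables 14.2.1.1, 14.2.2.1.1 and 14.2.2.2.1. The addendum's list of supplementary outputs omits these tables, so they would have to be reissued. If the Week 24 interim tables used chi-square, say so in 5.3.17 and state whether it was continuity-corrected.

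The cost is SAP wording, one program line and a rerun of three tables. The statistical price is that Fisher is more conservative: 78.0% power instead of 88.5% at 40/40, and 74.6-84.9% over the six splits, close to the approximately 80% the plan states.

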2.3.1 Eligibility and Randomization

Following completion of the screening activities, patients who meet the all the inclusion and none of the exclusion criteria will be registered by the Interactive Web Response System. Eligible patients will be randomly assigned in a 1:1 ratio to HepTcell or placebo treatment groups. Randomization will be stratified by study center to minimize imbalances between treatment groups.

The first 12 patients (6 HepTcell, 6 placebo) will form the sentinel cohort. To assure a 1:1 distribution of HepTcell and placebo in the sentinel cohort, randomization in this group will not be stratified.

If none of the Stopping Rules (see section 5.3.6.1) are met in one or more patients in the sentinel cohort, randomization may continue in the expanded study cohort.

The randomization list will be drawn up by an independent statistician.

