5.1 Sample Size

A study of IFN- α 2 in a population with inactive CHB reported a mean incremental decrease of 1.3 log-qHBsAg at 24 weeks in those patients completing IFN- α 2 treatment compared to non-treatment. Mean decrease would translate to approximately 50% of patients completing treatment achieving 1.3 log-qHBsAg response (reduction). To estimate treatment effect in the current study, the proportion of patients achieving a 1.0-log reduction in qHBsAg is estimated as one-half (25% of patients) who achieve this response. Assuming a response rate of 3% on placebo and 25% on HepTcell, 40 patients will be randomized per treatment group to detect a difference in the proportion of patients treated with HepTcell

achieving the primary endpoint compared to patient treated with placebo at a 0.05 level of significance (two-sided) with approximately 80% power.

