5.3.2.2 Secondary endpoints

The secondary efficacy endpoints are related to the evolution of serologic and viral markers as well as the PBMC ELISpot by days 85 and 169.

The secondary endpoints will be considered as described in section 4.2.2. Analyses to be performed are described in the following subsections.

No multiplicity adjustments will be made for secondary endpoints.

5.3.2.2.1 Proportion of patients achieving serologic clearance of HBsAg on Day 169

Patients who discontinue early or have missing HBsAg values on Day 169 but who achieve serologic clearance of HBsAg on the last available assessment prior to Day 169 will be treated as responders for this endpoint; otherwise, patients with early discontinuation or missing HBsAg values on Day 169 will be treated as non-responders.

The proportion of patients achieving serologic clearance of HBsAg on Day 169 will be estimated as follows:

(Number of patients having achieved serologic clearance of HBsAg on Day 169) / (Number of patients in the corresponding treatment (or overall)) x 100%

This proportion will be compared between treatment groups using Chi-Squared Test or Fisher's Exact Test at a 0.05% two-sided level of significance. Fisher's Exact Test will be used if the expected values of at least the 80% of the cells in the contingency table created for estimating proportions are lower than 5.

This proportion will be analyzed using logistic regression models with treatment group and baseline qHBsAg level as covariate. The analysis of maximum likelihood and odds ratio estimates for patients predicting a 'Yes' in achieving serologic clearance of HBsAg on Day 169 will be shown.

5.3.2.2.2 Proportion of patients achieving serologic clearance of HBV DNA on Day 169

Patients who discontinue early or have missing HBV DNA values on Day 169 but who achieve serologic clearance of HBV DNA on the last available assessment prior to Day 169 will be treated as responders for this endpoint; otherwise, patients with early discontinuation or missing HBV DNA values on Day 169 will be treated as non-responders.

The proportion of patients achieving serologic clearance of HBV DNA on Day 169 will be estimated as follows:

(Number of patients having achieved serologic clearance of HBV DNA on Day 169) / (Number of patients in the corresponding treatment (or overall)) x 100%

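### The logistic regressions for virologic response and HBsAg clearance have no rule for an arm without responders, which has a 29.6% chance on placebo under the plan's own assumptions

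*SAP*

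**What the plan says.** **Primary endpoint (SAP 5.3.2.1).** The responder proportions are first compared by a simple test: "This proportion will be compared between treatment groups using Chi-Square Test or Fisher's Exact Test". A logistic regression on treatment arm and baseline qHBsAg follows. Its output is described with the words "The analysis of maximum likelihood and odds ratio estimates for patients predicting a" positive result.

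**HBsAg clearance (SAP 5.3.2.2.1).** The same model is used: "This proportion will be analyzed using logistic regression models with treatment group and baseline qHBsAg level as covariate".

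**Planning assumptions (SAP 5.1, same text in Protocol 10.2).** "Assuming a response rate of 3% on placebo and 25% on HepTcell, 40 patients will be randomized per treatment group", tested "at a 0.05 level of significance (two-sided) with approximately 80% power".

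**Reporting (SAP Appendix 1).** The primary regression is Table 14.2.1.2 and the clearance regression is Table 14.2.2.1.2. Both are marked as top-line tables. For clearance, the plain summary of proportions (Table 14.2.2.1.1) is not marked.

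**What is absent.** Neither document mentions penalised likelihood, exact logistic regression, or any other rule for empty cells or separation. SAP 5.3.9, on missing data and outliers, has none either.

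**The concern.** With 3% expected on placebo and 40 patients, the plan expects 40 × 0.03 = 1.2 placebo responders. A count of zero is therefore an ordinary outcome.

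If it occurs, the data are quasi-completely separated by treatment. Lowering the intercept and raising the treatment coefficient by the same amount leaves every HepTcell prediction unchanged and always improves the fit to placebo. The likelihood keeps rising and has no maximum at a finite treatment effect, whatever baseline qHBsAg does. The software still prints something, but the odds ratio, its standard error and the Wald statistics then reflect the iteration limit, not the data.

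At stake is the only baseline-adjusted analysis that the SAP gives for the primary endpoint. For HBsAg clearance, it is the only result marked as top-line.

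**Working it through.** **Inputs.** Placebo 3%, HepTcell 25%, 40 per arm, two-sided 0.05 (SAP 5.1); 1:1 allocation (SAP 2.3.1); Fisher's test (Protocol 10.4.1). The documents give no dropout rate and no observed responder counts.

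**1. The plan's own figure.** Enumerating both binomials with two-sided Fisher at 0.05 gives power of 78.0%, close to the stated 80% or so. The assumptions are therefore read correctly.

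**2. Chance of no placebo responder.** P = (1 − p)^n.

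| Placebo rate | n | P(no placebo responder) |
|---|---|---|
| 3% (plan) | 40 | 0.97^40 = 29.6% |
| 5% (assumed) | 40 | 0.95^40 = 12.9% |
| 2% (assumed) | 40 | 0.98^40 = 44.6% |
| 1% (assumed) | 40 | 0.99^40 = 66.9% |
| 3% | 38 (assumed mITT size) | 31.4% |
| 3% | 36 (assumed mITT size) | 33.4% |

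**3. HBsAg clearance.** SAP 4.2.1 counts clearance as virologic response, so the placebo clearance rate q cannot exceed the placebo response rate. With q ≤ 3%, (1 − q)^40 ≥ 29.6%.

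**4. Does separation follow?** I simulated 3,000 trials at 3% and 25%, with baseline log10 qHBsAg uniform over 10 to 200 IU/mL and unrelated to response (assumptions). A linear-programming check found no finite estimate in 28.7% of them, the same share as had no placebo responder.

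**5. What the fit then shows.** Example: 0/40 on placebo, 10/40 on HepTcell, with a baseline covariate. Fisher p = 0.001. Newton iterations for the treatment coefficient:

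| Iteration | Log odds ratio | SE | Wald z |
|---|---|---|---|
| 5 | 5.08 | 3.53 | 1.44 |
| 10 | 10.08 | 42.8 | 0.24 |
| 20 | 20.08 | 6,352 | 0.003 |

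The coefficient rises by 1 per step without limit. The Wald p-value is about 0.15 at step 5 and 0.997 at step 20, from the same data. The likelihood-ratio chi-square settles at 14.9, so the information is present and only the Wald summary loses it.

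**6. The alternative.** A Firth fit to the same data is finite: log odds ratio 3.28 (SE 1.45), odds ratio about 27.

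**7. Where the failures fall.** At the planned rates, P(no placebo responder and Fisher p ≤ 0.05) = 0.283. As a share of Fisher-significant trials this is 0.283 / 0.780 = 36%. If both arms respond at an assumed 3%, the chance that at least one arm is empty is 1 − (1 − 0.2957)^2 = 50%.

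**The case against.** **No decision rests on this model.** The comparison of arms is the Chi-square or Fisher test, and the protocol compares "HepTcell and placebo groups using Fisher's Exact Test at a 0.05% two-sided level of significance". SAP 5.3 describes the study as exploratory and sets proof of concept at p < 0.05. Protocol 10.4.1 gives regression the task of examining baseline factors. This stands: separation cannot change the primary test. The regression tables are nevertheless marked as top-line, and the SAP asks for the treatment odds ratio in them.

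**The trial is over.** SAP section 2 reports that the Week 24 interim analysis found the primary and secondary endpoints not met and that the study is being terminated. A reader might infer from the 0/40 v 10/40 example that a significant Fisher result is being contradicted here by a non-significant regression. The documents do not support that, since the primary endpoint was not met. What remains is narrower: an empty arm would still leave the odds ratio undefined, and no counts are given to rule that out.

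**A reader might infer that the model fails precisely when the drug works.** It does not. About 64% of Fisher-significant trials at the planned rates have at least one placebo responder, and step 7 shows that a trial with no effect is also exposed.

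**A reader might take a Wald p near 1 as the size of the error.** It is only a stopping point. The SAP does not name Wald statistics either; I assume the usual table of maximum-likelihood estimates, which prints them.

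**A reader might extend the point to every binary model.** The HBsAg-loss model in SAP 5.3.3.14 has different terms and a different outcome definition, and for HBV DNA clearance no placebo rate is given. Neither was calculated, and the point does not cover them.

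**Conclusion.** The point holds for two regressions, virologic response and HBsAg clearance on Day 169. The plan specifies maximum likelihood with no rule for separation, although its own assumptions give a 29.6% planning-stage chance that the treatment odds ratio for the primary endpoint cannot be estimated. For clearance the chance is at least that.

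The figure rests on the assumed 3% rate and 40 patients per arm. It ranges from 12.9% at 5% to 66.9% at 1%, and neither of those rates is in the documents. The non-existence of the estimate, given an empty placebo arm, depends on no assumption about baseline qHBsAg.

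The damage is confined to the regression odds ratio, its Wald interval and its Wald p-value. The test of proportions and the decision to terminate the study are untouched. The point now concerns how the two tables are reported.

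**What to change.** For Tables 14.2.1.2 and 14.2.2.1.2, specify Firth penalised-likelihood logistic regression with profile-likelihood intervals, keeping the same terms. Exact logistic regression is an alternative. Because it conditions on a continuous baseline value, it may leave few possible data arrangements, so Firth is the easier choice.

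The Addendum describes its tables as supplementing those produced for Week 24, so outputs already exist. Check both fits for an arm without responders. If one is separated, mark the maximum-likelihood treatment estimate as not estimable, omit its Wald interval and p-value, and present the Firth result beside it, labelled post hoc.

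**Cost.** A changed model option and a footnote for two tables, plus some shrinkage of the odds ratio towards no effect. In a separated fit the shrinkage is not small, since an unbounded estimate becomes a finite one (about 27 in the example), and the table should say so.
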